## 5.2 Background on Nemolizumab

Nemolizumab (CD14152) is a humanized anti-human IL-31 receptor A monoclonal modified immunoglobulin G 2 antibody comprising a structure of 2 H-chains (445 amino acid residues) and 2 L-chains (214 amino acid residues) connected by 16 disulfide bonds. Nemolizumab inhibits the binding of IL-31 to IL-31 receptor A and subsequent transduction of the IL-31 signal into the cell.

### 5.2.1 Nonclinical Studies

The Investigator's Brochure (IB) contains detailed information on nonclinical studies.

### 5.2.2 Pharmacokinetic Profile

Nemolizumab PK profile was assessed in healthy volunteers and in subjects with AD after single and repeated doses with weight-based (0.1 mg/kg to 3 mg/kg) and flat (10 mg to 90 mg) doses. The PK profile of nemolizumab was also assessed in the Phase 2a study SPR.115828 with PN subjects, where a nemolizumab dose of 0.5 mg/kg was administered.

Overall PK assessments showed a dose proportional increase of nemolizumab serum concentrations after a single (mg/kg) injection and a less-than-proportional increase after repeated administrations of flat doses between 30 mg and 90 mg. Subcutaneous administration of nemolizumab results in slow absorption with peak serum concentrations achieved after 4 to 9 days. The terminal elimination half-life of nemolizumab was approximately 2 weeks after single and repeated administrations. No significant systemic accumulation was observed, and steady state concentrations were achieved from 16 weeks of treatment without a loading dose and from 4 weeks of treatment when a loading (flat 2×) dose was administered. The systemic exposure to nemolizumab appeared to be slightly lower in AD subjects compared to healthy volunteers.

Similar nemolizumab PK profiles were observed in subjects with AD and in subjects with PN. The similarity in nemolizumab exposure between the 2 populations was also confirmed using population PK modeling. The IB contains additional detailed information on the nemolizumab PK profile.

A low immunogenicity potential was observed in subjects with PN and in subjects with AD. No subjects had positive anti-drug antibodies (ADA) that included immunoglobulin E (IgE), and no subjects developed neutralizing antibodies. In both subject populations, concentration-time profiles and PK parameters of ADA-positive subjects were not different from the ADA-negative subjects.

### 5.2.3 Clinical Studies

The IB contains detailed information on clinical studies.

This document is confidential.

Studies have been completed in healthy subjects and subjects with AD, uremic pruritus, and PN (including the Phase 2a study RD.03.SPR.115828 and the Phase 3 pivotal study RD.06.SPR.203065).

Three additional Phase 3 studies in PN subjects are ongoing: 1 pivotal study (RD.06.SPR.202685), 1 long-term extension (LTE) study (RD.06.SPR.202699), and 1 dose optimization/long-term study (M525101-11) to assess the safety and efficacy of nemolizumab in subjects with a clinical diagnosis of PN.

There are also Phase 2 and Phase 3 studies in AD subjects, a Phase 3 study in subjects with pruritus associated with Chronic Kidney Disease and a Pharmacokinetic study for an Auto-Injector device ongoing.

### 5.3 Risk/Benefit Assessment

Pruritus is the cardinal symptom in PN and is often difficult to treat with current therapies. Chronic itching is believed to induce and maintain the characteristic PN skin lesions through an itch-scratch cycle. Therefore, the goal of PN treatments target pruritus remission to allow skin healing and improvement in patients' QoL.

Results of a previous clinical study with nemolizumab demonstrated a marked effect on both PN lesions and pruritus. The decrease in itching sensation was rapid, within the first week following the first injection and improved with subsequent administrations. This improvement in the signs and symptoms of PN was consistent with the observed improvement in QoL (evaluated using the Dermatology Life Quality Index [DLQI]). Continuous treatment with nemolizumab also led to an improvement in the overall severity of PN, which was evaluated with various scales (i.e., Investigator Global Assessment [IGA], Peak Pruritus [PP] Numeric Rating Scale [NRS], and Prurigo Activity Score). Based on the results of the Phase 2a study (RD.03.SPR.115828) nemolizumab was clinically and statistically significantly superior to placebo in reducing the weekly average of PP NRS scores at Week 4 (difference between treatment groups -38.0%; 95% confidence interval [CI] -51.0, -25.0;  $p<0.001$ ). The statistically significant improvements in IGA success and Prurigo Activity Score observed in the nemolizumab group were greater than those observed in the placebo group.

Based on the currently available information on nemolizumab and the risks associated with biologic agents in general, the important potential risks of nemolizumab treatment include local and systemic injection-related reactions, newly-diagnosed asthma or worsening of asthma, exacerbation of AD, and skin and non-skin infections.

The following specific risk-minimization and safety follow-up measures have been planned in this clinical study:

CD14152.RD.06.SPR.203890 Protocol V02 - 12Dec 3.0

- a. The protocol will exclude subjects who experienced an adverse event (AE) in the prior lead-in study that, in the opinion of the Investigator, could indicate continued treatment with nemolizumab would present an unreasonable risk for the subject.
- b. In the Phase 2b dose-ranging study (RD.03.SPR.114322) in AD, a dose-dependent increase of asthma flares (1 [1.8%], 2 [3.6%], 7 [12.3%], and 10 [17.5%] in placebo, 10-mg, 30-mg, and 90-mg treatment arms, respectively) in subjects with pre-existing asthma was observed. Events were mostly mild or moderate (1 severe event with highest dose), manageable, and reversible under treatment with study drug. At all visits, subjects with a history of asthma will complete a respiratory exam, the Asthma Control Test (ACT), and peak expiratory flow (PEF) testing. Subjects diagnosed with de novo asthma will complete respiratory assessments at all visits starting with the visit in which the diagnosis was confirmed. Subjects without a medical history of asthma will undergo periodic respiratory assessments. Subjects with a medical history of asthma will be referred to the physician managing their asthma if  $ACT \leq 19$ ,  $PEF < 80\%$  of the predicted value, and/or unexpected worsening of asthma is observed or reported. Subjects without a medical history of asthma will be referred to a respiratory specialist if respiratory changes suggestive of asthma are observed or reported and/or respiratory assessments suggest a decline in subject's health. An independent adjudication committee (IAC) will review all asthma AEs reported during the course of the study.
- c. As no data are available in pregnant or breastfeeding women, these patients are not eligible for this study.
- d. Patients who have recently received live or non-live vaccines may be considered for enrollment after an appropriate time has elapsed before baseline/Day 1 (Section 9.6.3). Administration of live vaccines is prohibited during the study. Administration of non-live vaccines is prohibited with the exception of seasonal, emergency, and coronavirus disease 2019 (COVID-19) vaccinations (Section 9.6.1). See [Appendix 1](#) for additional guidance for management of subjects and study conduct during the COVID-19 pandemic.
- e. A slight trend of dose-dependent increase of peripheral edema was reported in the nemolizumab Phase 2a study (CIM003JG) for AD. Most events were mild (11 of 21), no case was serious, and none resulted in premature treatment discontinuation; no case was associated with renal or cardiac AEs. Peripheral edema will be followed as an AE of special interest (AESI) in this study.
- f. An independent data monitoring committee (IDMC) will monitor the safety data regularly throughout the study, including AESIs listed in Section 12.7.2, which were defined based on the currently available safety information on nemolizumab and the risks associated with biologic agents in general.

In conclusion, when taking into consideration the currently available data of nemolizumab and the risk-minimization approaches to be implemented, the benefit/risk ratio of nemolizumab is considered to be favorable in this study.

#### **5.4 Dose Selection Rationale**

In the Phase 2 study (RD.03.SPR.115828), nemolizumab was tested as a 0.5 mg/kg subcutaneous (SC) injection administered Q4W in subjects with PN. The 0.5 mg/kg dose demonstrated efficacy in the treatment of PN with an acceptable safety profile and a very good immunogenicity profile.

The Phase 3 studies are conducted with a flat, fixed dose. The dose was selected with the aim of improving dosing convenience and avoiding potential errors that could be made while calculating, preparing, and/or administering a weight-based dose. The switch from weight-based dosing to a flat dose was based on an assessment of observed clinical data, and modeling & simulation tools.

Overall, subjects will continue to receive the same dose received in the LTE study (i.e., 1 or 2 SC injections of study drug administered Q4W). The dose was determined at baseline of the relevant lead-in study. Subjects with a body weight <90 kg were administered a 30 mg dose Q4W with a loading dose of 60 mg at baseline. Subjects weighing  $\geq 90$  kg were administered a 60 mg dose of nemolizumab Q4W (without loading dose). This dose adjustment was proposed to account for the impact of body weight on nemolizumab systemic exposure and subsequently to provide consistent efficacy response to nemolizumab across the body weight spectrum.

## 6 STUDY OBJECTIVES AND ENDPOINTS

### 6.1 Study Objectives

#### 6.1.1 Primary Objective

To assess the long-term durability of response over a 24-week period following withdrawal of nemolizumab in subjects with PN who previously responded to treatment in the LTE study RD.06.SPR.202699

#### 6.1.2 Secondary Objective

To assess the safety of nemolizumab compared to placebo over a 24-week period in subjects with PN who previously responded to treatment in the LTE study

### 6.2 Study Endpoints

#### 6.2.1 Primary Endpoint

Time from baseline to relapse, defined as meeting at least 1 of the following criteria:

- Increase in (weekly average of the) PP NRS score  $\geq 4$  points from baseline
- Increase in IGA score  $\geq 2$  points from baseline

The estimand of primary endpoint is defined as the following:

Estimand
Treatment: randomized treatment with subcutaneous injections of nemolizumab or placebo at Week 0, 4, 8, 12, 16, and 20
Population: all randomized subjects (intent-to-treat population)
Endpoint: time to relapse meeting at least 1 of the defined criteria
Intercurrent events: time to relapse will be censored at the last assessment of IGA and PP NRS prior to treatment discontinuation or use of prohibited medication
Summary measure: hazard ratio of nemolizumab and placebo

#### 6.2.2 Secondary Endpoints

##### 6.2.2.1 Efficacy Endpoints

The secondary efficacy endpoints include:

- Proportion of subjects with increase in PP NRS score  $\geq 4$  points from baseline at each scheduled visit

This document is confidential.

- Proportion of subjects maintaining IGA success, defined as IGA score of 0 (clear) or 1 (almost clear) at each scheduled visit
- Proportion of subjects with increase in IGA  $\geq 2$  points from baseline at each scheduled visit
- Absolute and percent change from baseline in PP NRS at each scheduled visit
- Absolute and percent change from baseline in Sleep Disturbance Numeric Rating Scale (SD NRS) at each scheduled visit
- Change from baseline in DLQI at Week 16 and Week 24

#### **6.2.2.2 Safety Endpoints**

The safety endpoints of this study are as follows:

- Incidence and severity of AEs, including treatment-emergent AEs (TEAEs), AESIs, serious AEs (SAEs), treatment-related AEs, and AEs that lead to discontinuation

## 7 INVESTIGATIONAL PLAN

### 7.1 Description of Overall Study Design and Plan

[figure not shown]
This is a Phase 3b multicenter, randomized, double-blind, placebo-controlled, parallel-group withdrawal study to evaluate the durability of response and safety of nemolizumab in adult subjects with PN who participated in the nemolizumab PN LTE study (RD.06.SPR.202699) and achieved a clinical response (i.e., IGA score of 0 or 1 and  $\geq 4$ -point improvement in weekly average of PP NRS score from baseline of the lead-in study) at Week 52 of the LTE study.

Subjects who agree to enroll in this study must do so at the time of completion of the Week 52 visit in the LTE study (RD.06.SPR.202699) to prevent any lapse in study treatment. After the Week 52 visit of the LTE study is complete, approximately 40 subjects who choose to enter this study will be randomized 1:1 to either continue the same dosing regimen received in the LTE study (i.e., 1 or 2 SC injections of study drug administered Q4W), or to discontinue nemolizumab and receive placebo.

Subjects' participation in the study will be up to approximately 32 weeks. The study consists of a 24-week treatment period and an 8-week follow-up period (12 weeks after their last study drug injection at Week 20).

Relapse is defined as an increase in (weekly average of the) PP NRS score  $\geq 4$  points from baseline or an increase in IGA score  $\geq 2$  from baseline at any point during the study. If a subject meets the criteria for relapse, then the subject may be considered for re-entry into the LTE study (RD.06.SPR.202699) (see [Figure 2](#)).

**Figure 2. Subject Transition between CD14152 Studies 202699 and 203890**

\*Clinical responder (CR) is defined as a subject with an Investigator Global Assessment (IGA) score= 0 or 1 and improvement in Peak Pruritus Numeric Rating Scale (PP NRS) score of  $\geq 4$  from baseline of the lead-in study at Week 52 visit of the long-term extension (LTE) study. Note: Lead-in study baseline is defined as baseline PP NRS score in the Phase 3 studies RD.06.SPR.202685 or RD.06.SPR.203065 for subjects who rolled over into the LTE from these studies. For subjects who entered the LTE study from the Phase 2 study RD.03.SPR.115828, the baseline PP NRS score at entry into the LTE study RD.06.SPR.202699 will be used.

\*\* Relapse is defined as an increase in weekly average of PP NRS score  $\geq 4$  points from baseline or an increase in IGA score  $\geq 2$  from baseline at any point during the study

See [Appendix 1](#) for additional guidance for management of subjects and study conduct during the COVID-19 pandemic.

### Baseline Assessment

After signing the informed consent form (ICF), all subjects will be evaluated for study participation, based on eligibility criteria. The study assessments at the time of completion of the Week 52 visit from the PN LTE lead-in study RD.06.SPR.202699 will be used as baseline assessments for the current study.

**Treatment Period**

Eligible subjects will be randomized to receive either 1 or 2 injections of nemolizumab or placebo according to their dosage group in the LTE study, as assigned by interactive response technology (IRT). Study drug will then be administered Q4W for 24 weeks with final dose administered at Week 20.

Refer to [Table 3](#) for a summary of study treatment.

**Table 3. Treatment Summary**

LTE Lead-in Study	Lead-in Study Assigned Treatment	Dose Q4W for 24 weeks a
RD.06.SPR.202699	Nemolizumab 30 mg (1 injection)	Blinded Nemolizumab 30 mg (1 injection)
	Nemolizumab 2 × 30 mg (2 injections)	Blinded Placebo (1 injection)
		Blinded Nemolizumab 2 × 30 mg (2 injections)
		Blinded 2 × Placebo (2 injections)

Abbreviation: LTE = long-term extension; Q4W = every 4 weeks.

aDose will be assigned based on dose received in LTE lead-in study.

Clinical assessments will occur according to the Schedule of Assessments in the protocol through the Week 24 visit.

If a subject meets the criteria for relapse at any point, the subject will exit the study and re-enter the LTE study (see [Figure 2](#)). Subjects who exit the study before Week 24 should complete an early termination (ET) visit. Subjects who complete the study through Week 24 are eligible to re-enroll in the LTE study.

Subjects who prematurely discontinue study drug for reasons other than relapse will be encouraged to complete the scheduled study visits. These subjects will only be eligible for re-enrollment in the LTE study if they continue with study visits through Week 24.

Subjects who discontinue the study for reasons other than relapse before Week 24 or who will not continue nemolizumab treatment in the LTE study should complete a follow-up visit, 12 weeks ( $\pm 7$  days) after the last study drug injection.

[figure not shown]

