**Table 2. Investigational Therapy**

	Investigational product	Comparator/Placebo
Name	Nemolizumab	CD14152 placebo
Internal code	CD14152	NA
Pharmaceutical form	Lyophilized powder for solution for injection supplied in a DCS	Lyophilized powder for solution for injection supplied in a DCS
Packaging	DCS packaged with a plunger rod (not assembled) and a 27G $\frac{1}{2}$ " safety needle	DCS packaged with a plunger rod (not assembled) and a 27G $\frac{1}{2}$ " safety needle
Storage conditions	Stored between 2°C to 8°C (36°F to 46°F); protected from freezing; protected from light	Stored between 2°C to 8°C (36°F to 46°F); protected from freezing; protected from light
Dosage a	30 mg (1 injection) or 60 mg (2 injections); see Table 1	1 injection or 2 injections; see Table 1
Route	SC use by subjects or clinic staff after reconstitution	SC use by subjects or clinic staff after reconstitution
Dose regimen	Q4W	Q4W
Treatment duration	24 weeks with last injection at Week 20	24 weeks with last injection at Week 20

Abbreviations: DCS = dual-chamber syringe (single use); NA = not applicable; Q4W = every 4 weeks; SC = subcutaneous.

a Subjects will receive blinded study medication as assigned by IRT, based on the assigned dosage in the lead-in LTE study RD.06.SPR.202699.

If a subject relapses (i.e., experiences an increase in PP NRS score of  $\geq 4$  points from baseline or an increase in IGA score  $\geq 2$  points from baseline), the subject will exit the study and will be eligible to re-enter the LTE study for active treatment (see [Figure 2](#)).

Treatment Duration:	The expected duration of each subject's participation in the study is up to 32 weeks, including a 24-week treatment period and an 8-week follow-up period (12-weeks after the last study drug injection).
Efficacy:	
The following efficacy assessments are planned according to the Schedule of Assessments (Table 7):
 
 
• IGA
 
• PP NRS
 
• SD NRS
 
 
The following quality of life assessment is planned according to the Schedule of Assessments (Table 7):
 
 
• Dermatology Life Quality Index (DLQI)
 

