8.4. Visit Windows

Efficacy by-visit summaries will use the analysis visit. All visits including unscheduled and early termination visits will be windowed based on the analysis visit window in [Table 8-1](#) which is based on study day. If multiple measurements are taken within the same window, the one taken closest to the target study day will be used for the analysis. If there are multiple measurements with same difference from target day, the later assessment should be used for the analysis.

Table 8-1: Analysis Visit Window

Analysis Visit	Target Study Day	Visit Window (IGA)	Visit Window (DLQI)
Baseline	1	≤ 1	≤ 1
Week 4	29	2 to 42	N/A
Week 8	57	43 to 70	N/A
Week 12	85	71 to 98	N/A
Week 16	113	99 to 126	2 to 140
Week 20	141	127 to 154	N/A
Week 24	169	155 to 210	141 to 210
Week 32 Follow-up	225	>211	N/A

All daily diary efficacy data will be classified into analysis visits as described in [Table 8-2](#) considering the data during the 7 days immediately preceding the target day of analysis visit.

Analysis visit of diary (ePRO) data will be defined depending on the data collection as below.

Consecutive daily assessment:

For the evening assessments (PP NRS), the daily data collected up to Week 24 will be classified into analysis visits considering the data during the 7 days immediately preceding the target study day of analysis visit. Similarly, for the morning assessment (SD NRS, morning sleep diary), the 7 days data up to the target study day will be classified into analysis visit. Details of the analysis visit window are in [Table 8-2](#) below.

This document is confidential.

Table 8-2: Analysis Visit Window for Evening and Morning Assessments

Analysis Visit	Target Study Day of Analysis Visit	Visit Window for evening assessment (PP NRS, AP NRS)	Visit Window for morning assessment (SD NRS, morning sleep diary)
Baseline	1	-7 to -1	-6 to 1
Week 1	8	1 to 7	2 to 8
Week 2	15	8 to 14	9 to 15
Week 3	22	15 to 21	16 to 22
Week 4	29	22 to 28	23 to 29
Week 5	36	29 to 35	30 to 36
Week 6	43	36 to 42	37 to 43
Week 7	50	43 to 49	44 to 50
Week 8	57	50 to 56	51 to 57
Week 9	64	57 to 63	58 to 64
Week 10	71	64 to 70	65 to 71
Week 11	78	71 to 77	72 to 78
Week 12	85	78 to 84	79 to 85
Week 13	92	85 to 91	86 to 92
Week 14	99	92 to 98	93 to 99
Week 15	106	99 to 105	100 to 106
Week 16	113	106 to 112	107 to 113
Week 17	120	113 to 119	114 to 120
Week 18	127	120 to 126	121 to 127
Week 19	134	127 to 133	128 to 134
Week 20	141	134 to 140	135 to 141

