Week 21	148	141 to 147	142 to 148
Week 22	155	148 to 154	149 to 155
Week 23	162	155 to 161	156 to 162
Week 24 ^a	169	162 to 175	163 to 176
Early Termination*	UN	7 days prior until Early termination visit (excluding early termination visit date)	6 days prior until early termination visit (including early termination visit date)

^a First 7 days data available will be used for weekly average calculation.

*For subjects with early termination, if weekly average is not available based on the slotting, additional analysis window was added and will be assigned to the week based on the slotting above. i.e., if subject

This document is confidential.

early terminated day 142, and week 21 is not available, the new window defined will be used to determine the weekly average at that week.

Safety and pharmacokinetics data will not be windowed for by-visit summary. i.e., scheduled visit data will be used for analysis.

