10.1. Primary Efficacy Endpoints

10.1.1. Primary Analysis of Primary Efficacy Endpoint

The primary endpoint is the time to relapse which is defined as meeting at least 1 of the following criteria:

- Increase in (weekly average of the) PP NRS score ≥ 4 points from baseline
- Increase in IGA score ≥ 2 points from baseline;

For primary endpoint, any subjects with missing data for PP NRS and IGA Score both at visit will be censored at the respective timepoint. If any one of PP NRS or IGA Score data is available for the visit, calculation for primary endpoint will be made using available results. If a subject has taken prohibited medication at any point of time during treatment period, then subject will be censored at the respective visit.

The primary endpoint will be analyzed using Cox proportional hazard model with treatment group, dosing regimen as a factor, and baseline PP NRS score and IGA score as covariates on ITT population. The estimated hazard ratio and the corresponding 95% CI will be presented. A supportive analysis also will be performed using Per-Protocol Population.

Kaplan-Meier survival plots will also be presented for time to relapse. The median time, 25th and 75th quantiles along with corresponding CI will be presented using ITT/PP.

Censoring rule for primary endpoint variable is as follows:

Situation	Date of Progression or Censoring	Outcome
Relapse as described	Date of Relapse	Event
Subject withdrawn without relapse	Date of last efficacy assessment (PP NRS and IGA) prior to withdrawal	Censored
Treatment Discontinuation	Date of last efficacy assessment (PP NRS and IGA) prior to Treatment Discontinuation	Censored
Prohibited medication without relapse	Date of last efficacy assessment (PP NRS and IGA) prior to prohibited medication	Censored
Completes the study without relapse	Date of Week 24 completion	Censored
No Efficacy assessment	Date of study Day 1	Censored

This document is confidential.

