10.2.2. Pruritus Numeric Rating Scale (NRS)

The Pruritus NRS is a scale to be used by the subjects to report the intensity of their pruritus (itch) during the last 24 hours. Peak pruritus (PP NRS) is an assessment of the maximum itch intensity in that period.

This document is confidential.

Subjects will be asked the following question:

- CCI

The Baseline PP NRS will be the score of Week 52 visit from LTE trial.

PP NRS at all follow-up visits will be determined as an average of 7 consecutive days data up to the target study day and will be set to missing if less than 4 days data are available. Subjects will receive instructions on how to record their PP NRS scores and will complete the assessment once daily in the evening throughout the clinical study (including the run-in and the follow-up period).

PP NRS will be determined by an average as described above at every week from Baseline to Week 24 as a continuous variable.

Descriptive summary of PP NRS (OC) will be provided on the ITT and Per-Protocol Populations. Absolute change and percent change from Baseline for the PP NRS will also be included in the summary on the ITT and Per-Protocol Populations.

Absolute change from Baseline in PP NRS will be analyzed using ANCOVA based on OC, including treatment group dose regimen as factors with baseline value as covariate. The least squares means (LSMeans), standard error of LSMeans, and 95% CI for change from baseline, as well as the difference in LSMeans between the treatment groups, the two-sided 95% CI, and associated p-value will be presented. Percentage change from Baseline in PP NRS will not be analyzed because of the small sample size and potential high skewness of the data.

The analysis will be repeated:

- on Per-Protocol Population, based on OC

on ITT population, based on OC and using MMRM approach, including treatment group and dose regimen as factor, visit, interaction term between treatment and visit, and baseline value as covariate. Kenward-Roger approximation is used to estimate denominator degrees of freedom. An unstructured covariance is used to model the within-patient errors in the analysis. While applying the model, if convergence criteria not met with unstructured covariance matrix, then below mentioned covariance matrix will be applied to achieve convergence of the model. The matrix with the minimum AIC criteria will be selected for the further analysis.

- Compound Symmetry (CS)
- Ar(1) – Autoregressive (1)

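### A relapse that takes a subject out of the study can be censored by the SAP's derivation of the primary event, and no sensitivity analysis counts it

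*Protocol*

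**What the plan says.** **Exit.** Protocol 7.1, after Table 3, states: "If a subject meets the criteria for relapse at any point, the subject will exit the study and re-enter the LTE study". The synopsis says the same for the treatment period, and after Table 2 adds that "the subject will exit the study and will be eligible to re-enter the LTE study for active treatment". Earlier in 7.1 the wording is softer: "then the subject may be considered for re-entry into the LTE study". Section 10.3.1 speaks only of eligibility to re-enter. Protocol 8.3 lists treatment failure, with a reference to subjects who relapse, among the reasons for stopping study drug.

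**Criterion.** The synopsis endpoints, Protocol 6.2.1, 7.1 and 14.3.1, and SAP 5.1 and 10.1.1 agree: a rise from baseline of at least 4 points in weekly average PP NRS, or of at least 2 points in IGA. The text after Table 2 is the exception. It begins "If a subject relapses (i.e., experiences an increase in PP NRS score of" and gives the 4-point figure without mentioning a weekly average.

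**PP NRS in the SAP.** Table 8-2 assigns diary days to fixed study-day weeks. Under SAP 10.2.2 the weekly value "will be set to missing if less than 4 days data are available". For early termination, the footnote to Table 8-2 says: "if weekly average is not available based on the slotting, additional analysis window was added".

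**IGA in the SAP.** Section 8.4 assigns all visits, including ET and unscheduled ones, to the windows of Table 8-1. "If multiple measurements are taken within the same window, the one taken closest to the target study day will be used for the analysis". The section introduces this for by-visit efficacy summaries.

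**Event and censoring.** SAP 10.1.1 calculates the endpoint from whichever of the two scores is available at the visit. It dates an event at the date of relapse, which it does not define. Its censored rows include "Subject withdrawn without relapse" and treatment discontinuation; the second carries no condition that relapse be absent. SAP Table 7-1 also censors data collected after treatment discontinuation. The three sensitivity analyses in SAP 10.1.2 concern the per-protocol population, actual strata and COVID-19-affected visits.

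**The concern.** Relapse is both the primary event and the trigger that ends observation. The decision to exit is taken during the study; the event is derived afterwards. If the two do not use the same days, the same minimum number of entries and the same IGA readings, a subject can leave because of relapse and still have no event in the SAP. That subject is then censored just as the disease worsens, and no later data in this study can correct it.

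The main quantity at risk is the relapse curve on placebo. Protocol 7.2 says the study is meant to show how long the effect lasts once treatment is removed, and the placebo arm answers that. With about 40 subjects planned and no formal sample size calculation, a few lost events are a material share.

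**Working it through.** The plan gives no power, event count or relapse rate, so there is no figure of its own to reproduce. The check is of the derivation rules, followed by an illustration of size.

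**1. How a PP NRS relapse can be missed.** Take an ET visit on Day 41. The Week 6 slot is Days 36 to 42, so Days 36 to 40 supply up to 5 entries. With at least 4, the week is available and the ET window is not used. That window would be Days 34 to 40. Let *a* be the mean of Days 34 and 35, and *b* the mean of Days 36 to 40. The pre-ET mean is (2*a* + 5*b*)/7; the SAP uses *b* alone. If *a* exceeds *b*, the pre-ET mean can reach +4 while *b* does not. In Week 5 (Days 29 to 35), *a* is diluted by five earlier days. Neither slot then shows a relapse.

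**2. How often, under assumptions.** Simulated diaries had daily SD 1.0 or 1.5, a rise of 0.1 or 0.3 points per day to a plateau of +4.5 or +6, 15% missed days, and ET 0 or 7 days after the trigger. The share of relapse exits with no SAP event was:

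| Rule assumed for the exit decision | Share missed |
|---|---|
| The SAP's fixed weeks | 0% |
| Rolling 7-day mean | 0 to 15% |
| One daily score | 24 to 100% |

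The upper end for the rolling mean is not firm. With other assumed trajectories, 90% diary completion and ET within 5 days, two runs gave 11 to 14% and 15 to 21%. At 60% completion with no minimum number of entries, the share was 38 to 48%. Requiring at least 4 entries reduced it to under 1% for same-day exit and 18 to 20% for delayed ET.

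**3. How an IGA relapse can be missed.** Week 8 has target Day 57 and window Days 43 to 70. With a visit on Day 57 at IGA 1 and an exit on Day 66 at IGA 3, Day 57 is nearer the target and the IGA of 3 is discarded. This holds for any ET or unscheduled IGA on Days 58 to 70, which is 1 to 13 days after an on-target visit. When the scheduled visit is at the edge of its allowed window, 8 to 12 days are affected. For observed-case by-visit IGA analyses the loss is certain. For the primary endpoint it occurs only if the window rule also governs time to relapse, which SAP 10.1.1 leaves open.

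**4. What happens to a missed exit.** It is not an event under the derivation, so the withdrawal and treatment-discontinuation rows remain, both censored. Because the second row is unconditional and relapse is a reason to stop drug, it could on a literal reading catch even a relapse that the derivation finds. None of the three sensitivity analyses restores these exits.

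**5. Size of the effect.** Assumed: 20 subjects per arm, constant proportional hazards, and 24-week relapse *p*(P) on placebo and *p*(N) on nemolizumab.

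- HR = ln(1 − *p*(N)) / ln(1 − *p*(P)).
- Events *d* = 20*p*(P) + 20*p*(N).
- Power = Φ(|ln HR| × √(*d*/4) − 1.96).
- If a fraction *f* of relapse exits is censored, *d* becomes (1 − *f*)*d* and the placebo Kaplan-Meier relapse estimate becomes 1 − (1 − *p*(P))^(1 − *f*).

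The last three columns show *f* = 0 / 10% / 20%, with equal loss in both arms:

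| Placebo vs nemolizumab | HR | Events | Power | Placebo estimate |
|---|---|---|---|---|
| 40% vs 10% | 0.21 | 10 / 9 / 8 | 70 / 66 / 61% | 40 / 37 / 34% |
| 60% vs 15% | 0.18 | 15 / 13.5 / 12 | 92 / 89 / 85% | 60 / 56 / 52% |
| 70% vs 30% | 0.30 | 20 / 18 / 16 | 78 / 73 / 68% | 70 / 66 / 62% |

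Example: 1 − 0.4^0.9 = 0.56. With equal loss the HR does not change. If only placebo loses 20%, it becomes HR/0.8: 0.26, 0.22 and 0.37. The 20% column lies above the 0 to 15% range in step 2 and is a stress case. SAP 4.1 mentions about 100 subjects, against 40 in SAP 4.3 and Protocol 14.1. At 100, power stays at 94% or more with a 20% loss, but the downward shift of the placebo estimate is the same.

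**The case against.** The strongest reply is that the SAP does reproduce the protocol's relapse rule. The thresholds match almost everywhere, ET and unscheduled IGA scores are kept in the data, and an ET diary window exists. The event row comes first in the censoring table, and a natural reading gives it precedence. Windowing is introduced for by-visit summaries, and nearest-to-target is conventional there. The ITT analysis that imputes missing as relapse counts visits missing after exit as relapses. All of this stands, and it limits the point to specific gaps.

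A reader might infer more than the documents support:

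- **A single bad day triggers exit.** Only the text after Table 2 omits the weekly average, and the same synopsis states it in full. That passage needs reconciling; it does not establish a single-score rule.
- **About half of IGA relapses are lost.** Days 58 to 70 are 13 of the 27 days between on-target visits (48%), but that is a share of calendar days. IGA is scheduled only at visits, and a relapse found at the scheduled visit used for its window is retained.
- **The hazard ratio is pulled towards 1.** More exits on placebo does not mean that a larger fraction of them is missed.
- **Sites apply their own averaging rule.** The text does not say who declares a PP NRS relapse. Protocol 11.2.1 is partly redacted and the transition figure is not shown, so the absence of a rule cannot be fully established.

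**Conclusion.** The concern holds as a gap in event capture. A relapse that ends observation can go unrecognised by the SAP's derivation, can then only be censored, and is not restored by any planned sensitivity analysis.

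The size is uncertain. For PP NRS it is nil if exit decisions use the SAP's weeks and about 0 to 15% of relapse exits under a rolling weekly mean. It is clearly larger only with sparse diaries or the literal single-score wording. These percentages rest on assumed itch courses. For IGA the loss is certain in observed-case by-visit output, which is the only version planned for the per-protocol population, and only possible for the primary endpoint.

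Any loss biases the placebo relapse curve downwards. A bias in the hazard ratio needs unequal loss between arms, which the documents neither show nor exclude. The point is worth correcting before unblinding, but it does not show that the primary analysis is invalid.

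**What to change.** In SAP 10.1.1:

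1. Derive relapse and its date from all dated post-baseline assessments, including ET and unscheduled IGA. The nearest-to-target rule can stay for by-visit summaries.
2. Evaluate the 7-day pre-ET PP NRS average for every early termination, whether or not the slotted week is available.
3. State that relapse takes precedence over the withdrawal and treatment-discontinuation rows.

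In SAP 10.1.2, add a sensitivity analysis that counts each exit recorded as relapse as an event on its exit date. Protocol 8.3 already has the withdrawal reason recorded in the eCRF; the sponsor should confirm that the form identifies relapse.

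In the protocol, the sponsor must reconcile the text after Table 2 with the synopsis endpoints and sections 6.2.1, 7.1 and 14.3.1 on the PP NRS criterion. It must also reconcile the wording that a relapsing subject will exit with the softer wording in 7.1 and 10.3.1. Exit and analysis should then rest on one definition; which one is for the sponsor to decide.

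The cost is a few SAP sentences, one extra model run and a protocol clarification. The drawback is that the added analysis may count some exits that did not meet the weekly-average criterion, so it should remain a sensitivity analysis.
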